4.2 Secondary Subjects

N/A

4.3 Number of Subjects

A. Total Number of Subjects

50 MS patients and 50 healthy donors will be enrolled in this study. Please refer to section “1.5 Sample Size Justification” for calculation regarding sample size.

B. Total Number of Subjects If Multicenter Study – N/A

C. Feasibility

RWJ MS Center evaluates enough newly diagnosed MS patients every year to be able to recruit 50 MS patients for the study over 1 years. 50 healthy volunteers will be recruited from Rutgers students/staff and New Jersey local resident..

4.4 Consent Procedures

A. Consent Process

▪ Location of Consent Process

Rutgers – Robert Wood Johnson Medical Group
RMJ Multiple Sclerosis Center,
[name]

▪ Individual Roles for Researchers Involved in Consent

[name] [name] &/ or [name], APN, MSCN (study coordinator) will be the only 2 individuals who will obtain informed consent from study participants.

▪ Consent Discussion Duration

Consent discussion will take place until the subject is fully aware of all study details and all questions have been answered. There is no set time for consent discussion.

▪ Coercion or Undue Influence

Subjects will not be coerced to participate. Participation is voluntary and will not interfere with any current or future medical care at the MS Center.

▪ Subject Understanding

Subjects will be able to read / review the consent in its entirety. Study participation and expectations will be fully and clearly explained. The timeline of study will also be explained. Subjects will have all questions answered prior to signing of the informed consent. Subjects will receive a copy of the signed / dated informed consent.

B. Waiver or Alteration of Consent Process

N/A

C. Documentation of Consent

▪ **Documenting Consent**

The study will be explained to the subject by the investigator and/or study coordinator. The subject will be allowed time to read the consent. All subject's questions will be answered. The subject and investigator and/or study coordinator will sign the consent form. A dated and signed copy will be given to the subject.

4.5 Special Consent/Populations

N/A

4.6 Economic Burden and/or Compensation for Subjects

A. Expenses

Subjects will not incur any expense

B. Compensation/Incentives

Both MS patient and healthy volunteers will be compensated in the amount of \$100 for travel reimbursement.

C. Compensation Documentation

A dated log will be kept to document subject compensation.

4.7 Risks of Harm/Potential for Benefits to Subjects

A. Description of Risks of Harm to Subjects

▪ **Reasonably Foreseeable Risks of Harm**

- Risk of potential loss of subject privacy due to collection of medical information.
- The most encountered side effect of venipuncture is bruising at the site of the needle puncture up to an excessive bleeding and infection, all of which will be minimized by using a sterile technique.
- Collection of fecal samples at home may impose inconvenience for the participants and/or their families.

- Participants may experience gastrointestinal symptoms (e.g. bloating, flatulence, diarrhea, constipation or cramping) when they consume HFS. These discomforts are common; however, these discomforts are minor and they should not last longer than a few hours.

B. Procedures which Risk Harm to Embryo, Fetus, and/or Pregnant Subjects

Pregnant females will be excluded from the study.

▪ Provisions to Protect the Privacy Interests of Subjects

The study investigators will be utilizing Rutgers University REDCap (research electronic data capture). REDCap is a secure web application designed to support data capture for clinical studies. REDCap is a suitable method for data entry, editing, and quality assurance. This web application will be used to keep patient information secure

C. Potential Benefits to Subjects

HFS can promote the growth of healthy bacteria including SCFAs-producers in the gut, and the growth of SCFAs-producing gut bacteria can help the development of regulatory cells. Therefore, consumption of high-fiber supplement could be beneficial therapeutic supplement to disease modifying drugs in halting MS progression.

5.0 Special Considerations

5.1. Life style consideration

Since the risks of study drug on embryofetal development are unknown, participants in Group A and Group C will be required to use contraception methods.

Men and women of childbearing potential participating in this study will be required to use contraception from study recruitment until 30 days after the last day of study participation. Acceptable forms of contraception:

For men with female partners of childbearing potential:

1. Agree to use male condom.
2. Abstinence is an acceptable method only if it is consistent with the preferred and usual lifestyle of the patient

For women of childbearing potential:

1. Agree to use highly effective contraception method below:
 - 1-1. Combined (estrogen and progesterone-containing) hormonal contraception by oral, intravaginal, or transdermal method.
 - 1-2. Progesterone-only hormonal contraception by oral or injectable method.
 - 1-3. Intrauterine device.
 - 1-4. Bilateral tubal occlusion.

1-5. Vasectomized partner.

2. Abstinence is an acceptable method only if it is consistent with the preferred and usual lifestyle of the patient.

Men should refrain from donating sperm and women from donating eggs during the specified duration as well.

5.2 Health Insurance Portability and Accountability Act (HIPAA)

To gather information in regard to a subject's medical history the following information may be necessary to access. This will pertain to subjects with Multiple Sclerosis.

- Information in your medical record
- Hospital discharge summaries
- Radiology records or images (MRI, CT, PET scans)
- Medical history or treatment
- Medications
- Laboratory/diagnostic tests or imaging

Healthy donors will also be asked name, gender, date of birth, and medical history (to make sure they are eligible for the study).

5.3 Family Educational Rights and Privacy Act (FERPA)

N/A

5.4 NJ Access to Medical Research Act (Surrogate Consent)

N/A

5.5 General Data Protection Regulation (GDPR)

N/A

5.6 Code of Federal Regulations Title 45 Part 46 (Vulnerable Populations)

A. Special Populations

N/A

6.0 Data Management Plan

6.1 Data Analysis

6.2 Data Security

1. The study investigators will be utilizing Rutgers University REDCap (research electronic data capture). REDCap is a secure web application designed to support data capture for clinical studies.
2. Data will be stored in password protected computers and only authorized person involved in study will have access.
3. Data will be transferred via encrypted emails and password protected portable storage device.

6.3 Data and Safety Monitoring

Data/Safety Monitoring Plan

A. Periodic Data Evaluation

Data will be accessed every month.

B. Type of Data Evaluated

1. Fecal sample 16S rRNA sequencing.
2. Gut permeability.
3. Cytokine production.
4. Development of pathogenic and regulatory immune cells.

C. Collection of Safety Information

- Details regarding allergic reactions and intolerance to ingredients of the fiber supplement.
- MS patients and HDs on HFS will be monitored for side effects such as nausea, excessive gas, loose stools, and diarrhea during first week of intervention and every month thereafter throughout the intervention.

D. Frequency of Data Collection

We will collect the research and safety data every two weeks. We will start the safety data collection when patients visit our clinical center for this study.

E. Reviewer of Data

[name], [name], and [name] [name]

F. Schedule Of Review Of Cumulative Data

Data will be accessed every month.

G. Tests for Safety Data

Potential side effects by ingestion of HFS such as nausea, excessive gas, loose stools, and diarrhea will be monitored.

[name] and [name], APN, MSCN will analyze safety data to determine whether harm is occurring. Appropriate medical referrals will be made if necessary.

H. Suspension of Research

In the event a study participant develops a severe allergic reaction or any other adverse reaction to HFS, this individual will be required to no longer participate in the study. Also, if any personal study subject information is leaked, they will be removed from the study.

A. Data/Safety Monitoring Board Details

N/A

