During the baseline visit, all MS patients and HDs will provide a blood and stool sample. For MS patients and HDs who are in the HFS group, they will be provided with supplies and instructions to take the supplement (Appendix 5). All the participants will be provided with stool kits and instruction on stool collection. Stool samples will be collected at home and transported to the laboratory by the participant in Piscataway for analysis.

Group A and Group C: MS patients in Group A and HDs in Group C will consume supplement orally as a drink two times a day to ensure fiber intake of 60 g/day for 12 weeks (High-fiber supplement group, Group A), as shown in [name] T2DM study (1). Participants will gradually increase the dosage of supplement over several days to mitigate the potential tolerability issues,

starting with daily consumption of 30g/day for first 5 days and then increasing to targeted daily consumption of 60g/day.

A member of the research team will follow up by phone at the end of the first week to check for compliance and adverse effects and then every month thereafter (Appendix 6). Patients will receive the fiber supplement in individual sachet (30g/sachet) by mail every two weeks, and they will be asked to return any unused supplement in their next study visit. Since the risks of study drug on embryofetal development are unknown, participants in Group A and Group C will be required to use contraception methods. Please refer section 5 special considerations for more details.

At baseline, Week 8 and week 12, 6 samples (3 blood and 3 fecal sample) will be collected from each subject.

All MS patients will be followed prospectively, and one more blood and one more fecal sample will be collected during relapse (before steroid treatment) and upon symptom resolution, and examined for intestinal inflammation, permeability, and microbial composition. The concentration of intestinal inflammation biomarkers in feces including Lcn-2, Calprotectin, and Lactoferrin, and a biomarker for intestinal permeability, serum zonulin, will be measured by ELISA assay.

As a control we will also analyze these biomarkers in the fecal samples isolated from healthy donors (n=25) in **Group C** and **Group D**. Healthy donors will be asked to provide 3 blood and 3 stool samples over the course of 12 weeks (baseline, week 8, and week 12).

Group E will consist of 25 subjects with MS who experience an MS flare up.

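### The reaction rule in 6.3 H ends study participation, not just the supplement, and sets no clear threshold for reactions other than severe allergy

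*Combined protocol and SAP*

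**What the plan says.** Section 6.3 H (Suspension of Research) applies to a participant who "develops a severe allergic reaction or any other adverse reaction to HFS, this individual will be required to no longer participate in the study". The next sentence deals with data leaks: "if any personal study subject information is leaked, they will be removed from the study". Both sentences therefore describe leaving the study.

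Other sections bear on how the rule would work:

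- **4.7** lists bloating, flatulence, diarrhea, constipation and cramping as foreseeable on HFS and adds: "These discomforts are common; however, these discomforts are minor and they should not last longer than a few hours".
- **1.3 A** starts at 30 g/day for 5 days and then goes to 60 g/day: "Participants will gradually increase the dosage of supplement over several days to mitigate the potential tolerability issues". A call at the end of week 1 is made "to check for compliance and adverse effects and then every month thereafter".
- **6.3 C** monitors HFS users for side effects such as nausea, gas, loose stools and "diarrhea during first week of intervention and every month thereafter throughout the intervention".
- **6.3 G** has two named staff who "will analyze safety data to determine whether harm is occurring".
- **1.3 A** plans that at baseline, week 8 and week 12, "6 samples (3 blood and 3 fecal sample) will be collected from each subject".
- **1.3 D** defines the primary endpoint as the change from before to after HFS in 25 MS patients.
- **1.3** gives HFS to Groups A and C only.

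**The concern.** There are two problems in one sentence.

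First, the threshold is unclear. The word *severe* is attached to allergic reactions, and no grade is attached to other reactions. Taken at its word, the rule would remove people for symptoms that the rest of the protocol expects, calls minor, and plans to follow through the whole intervention. Two members of staff could apply it differently.

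Second, the consequence is leaving the study rather than stopping the supplement. The text shown does not describe stopping HFS while staying in follow-up, reducing the dose, or taking a sample at withdrawal. That removed participants give no later samples is an inference, but it is the plain meaning of no longer participating.

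At stake is who contributes to the primary endpoint. People who react to fiber may differ in microbial or immune response. If their later samples are missing, the Group A change describes only those who tolerated HFS. Groups B and D take no HFS, so the reaction clause cannot produce a matching loss there.

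**Working it through.** **Step 1: which samples are at risk.** Reactions can come to light at the week 1 call or at the monthly calls.

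- Removal at week 1 or at the first monthly call: the week 8 and week 12 samples are lost.
- Removal after week 8: the week 12 samples are lost.
- Samples already given are unaffected.

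**Step 2: two readings of the threshold.**

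- *Literal:* any reaction counts. This conflicts with 4.7, with the ramp-up, and with continued symptom monitoring in 6.3 C.
- *Narrow:* only harmful reactions count. The word *severe* and the harm judgement in 6.3 G support this. Section 4.1 excludes self-reported allergy or intolerance to the ingredients and gastrointestinal disorders, and 1.7 describes the HFS as well tolerated. Few removals would then be expected.

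The consequence, leaving the study, is the same on both readings.

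**Step 3: the plan's own figure.** Section 1.5 gives n=20 per group at 5% type I error and 80% power, and enrols 25. It states no mean difference, SD or sidedness, so the 20 cannot be reproduced. I take it as exactly 80% power, two-sided, and solve for the effect:

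- paired t-test, 20 pairs: standardized change 0.660;
- two-sample t-test, 20 v 20: standardized difference 0.909.

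Using the n=20 from 1.5 for a paired test is itself an assumption.

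**Step 4: precision if removed participants are lost.** The documents give no reaction rate, so the rates q are assumed. The number left in Group A is 25 × (1 − q). For A v B, Group B stays at 25.

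| q | left in A | before/after power | A v B power |
|---|---|---|---|
| 0 | 25 | 0.886 | 0.883 |
| 4% (1 of 25) | 24 | 0.872 | 0.876 |
| 10% | 22.5 | 0.849 | 0.865 |
| 20% | 20 | 0.800 | 0.842 |
| 30% | 17.5 | 0.739 | 0.812 |
| 40% | 15 | 0.663 | 0.774 |

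The before/after column matches the primary endpoint. It reaches 80% at 20% loss, because 25 × 0.8 = 20. The A v B comparison stays above 80% at 30% loss.

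**Step 5: selection.** The shift in Group A's mean change is q × (mean change in remaining − mean change in removed). With an assumed difference of 0.5 SD:

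- 0.04 × 0.5 = 0.02 SD for 1 of 25;
- 0.05, 0.10, 0.15 and 0.20 SD at 10, 20, 30 and 40%.

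The 0.5 SD has no source in the documents, and the sign could go either way.

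**Step 6: dilution if stoppers are kept and pooled.** If stoppers show no effect and the SD is unchanged, the standardized change becomes 0.660 × (1 − q) with 25 pairs. At 20% this is 0.660 × 0.8 = 0.528, with power 0.72, against 0.80 if they are lost. At 10% it is 0.594, with power 0.81, against 0.85. Retaining samples therefore does not by itself make pooling them the better main analysis.

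**The case against.** The strongest reply is that the literal reading is not what the authors mean. The protocol treats gut symptoms as expected, ramps the dose to manage them, screens out intolerance and gut disorders, and asks staff to judge harm. On that reading perhaps one person in 25 leaves, the assumed shift is 0.02 SD, and before/after power moves from 0.886 to 0.872. This stands: the practical effect is then probably small. It does not clear the sentence, because staff have to apply what is written and the separation of supplement from study is missing on both readings.

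A second reply is that this is a mechanistic study of consuming HFS. Table 1 labels its visits as weeks after HFS, so a week 12 sample from someone who stopped in week 1 says little about intake. Nor does any text shown say that A and B are randomised, so preserving randomisation cannot be used to argue for an all-participant analysis. This also stands, and it is why pooling is not proposed as the main analysis. It leaves intact the use of retained samples to see whether stoppers differ.

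Third, handling after removal may be described in the consent forms or the appendices, which are not available here. The point is limited to the text shown.

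A reader might infer three stronger claims that the documents do not support:

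- *The primary result will be biased.* No reaction rate is given, and nothing shows that reactors respond differently.
- *All removals fall on A and C.* That is true of the reaction clause only. The data-leak clause in 6.3 H can remove someone from any group.
- *The study will be underpowered.* Loss would have to exceed about 20% for the before/after comparison, and that threshold rests on the back-solved effect.

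**Conclusion.** The point holds as a wording defect with a possible cost. As written, 6.3 H conflicts with 4.7 and the ramp-up, and it turns a reason to stop the supplement into a reason to leave the study. It can therefore cause selective, one-sided loss of week 8 and week 12 samples in the primary endpoint.

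The size and direction are unknown. If only harmful reactions are meant, the effect is probably small. If the literal rule were applied and 20 to 40% left, before/after power would be about 0.80 to 0.66. These figures assume the loss rates, a two-sided paired test, and that n=20 gives exactly 80% power. The selection figures also assume a 0.5 SD difference.

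This is worth the investigators' consideration. It does not show that the design fails.

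**What to change.** Amend 6.3 H in two ways:

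1. Limit mandatory stopping of HFS to allergic, severe or harmful reactions, as judged by the investigators under 6.3 G.
2. State that stopping HFS does not end participation. Unless consent is withdrawn or sampling is unsafe, collect the scheduled week 8 and week 12 stool and blood, and record the stop date and reason.

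The cost is protocol wording, and consent wording if the form repeats the rule. No visits are added. Safety is not weakened, because HFS still stops for harmful reactions.

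The statistical downside is dilution if off-supplement samples are pooled into the main analysis. The on-supplement before/after change may therefore remain the main result, with the retained samples used to check whether those who stopped differ. The on-supplement result still carries the selection, but the retained samples make it possible to examine.

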1.5 Sample Size Justification

Our collaborator, [name] employed n = 27 in the HFS-treated group and n=16 in non-treated group and observed a significant effect of HFS on SCFA production in type 2 diabetes mellitus (T2DM) study (1). Since the therapeutic effect of HFS may be different between MS and T2DM, we sought the assistance of [name] who is a Biostatistician at Rutgers University. We selected the published MS studies that showed the effect of high vegetable diet on development of Tregs (n=10 in each group in this study) (12), and calculated a reasonable sample size using mean and standard deviation of the data, assuming a mean difference of 5% type I error and 80% power. Our sample size calculation indicated that n=20 in each group is sufficient to observe the statistical difference in the development of regulatory cells. Although there is no published data on the effect of diet on intestinal permeability in MS, a study of intestinal permeability in MS (n=14) vs healthy donor (HD) (n=16) showed statistically significant increase in intestinal permeability in MS patients compared to HD (8). Our sample size calculation also indicated that n=20 in each group is sufficient to observe a statistical difference. Based on our previous HFS-data and sample size calculation, we propose to enrol 25 patients in each group in Aim-1. Regarding the sample size in Aim-3, there is no published intestinal inflammation biomarker data in MS. Therefore, we used the data from an IBD study (20) where n=20 was sufficient to detect

differences in Lcn-2, lactoferrin, and zonulin between IBD vs HD. From our sample size calculation we propose to enroll 25 patients in each group in Aim-3.

Summary:

Stool, and blood samples isolated from 50 MS patients and 50 healthy controls will be used for gut permeability, bacteria DNA sequencing, immunology experiments, and MS animal experiments.

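### Section 6.3 H answers a leak of personal information by removing, on its natural reading, the affected participant; this contains nothing and ends remaining sampling for a study-side fault.

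*Combined protocol and SAP*

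**What the plan says.** Section 6.3 H (Suspension of Research) holds two removal rules. The first concerns a participant who has a severe allergic or other adverse reaction to HFS: "this individual will be required to no longer participate in the study". The second follows directly, joined by *Also*: "if any personal study subject information is leaked, they will be removed from the study". The second rule has no threshold of seriousness, no limit on numbers and no role for the participant's own choice. It does not say what happens to samples and data already collected. Despite its title, the section gives no condition for suspending the research or a data route.

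Section 4.7 A opens its list of foreseeable risks with "Risk of potential loss of subject privacy due to collection of medical information". The protection named in section 4.7 is REDCap. Section 6.2 adds password-protected computers, access for authorized staff only, and this on transfer: "Data will be transferred via encrypted emails and password protected portable storage device". All of these are preventive. The sections available for review state no response to a leak other than removal.

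On group size, section 1.5 reports that "n=20 in each group is sufficient to observe the statistical difference in the development of regulatory cells" and then that "we propose to enrol 25 patients in each group in Aim-1".

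**The concern.** A leak is a failure of the study's data handling. Removing the person harmed does not retrieve the information, close the route by which it escaped, or tell anyone that it happened. It does end the rest of that person's scheduled sampling. Each participant gives stool and blood at baseline, week 8 and week 12, and the primary endpoint in section 1.3 D compares MS patients before and after HFS. A person removed before week 8 contributes no post-baseline sample; one removed between weeks 8 and 12 lacks the last. The loss would have nothing to do with treatment or outcome and would be avoidable. Because the rule is mandatory and has no limit, one event that exposed several records would oblige the study to remove all of those people.

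**Working it through.** **Who is removed.** In section 6.3 H the adverse-reaction rule has a single participant as its subject. The leak rule is joined to it by *Also* and uses *they*, with study subject as the only nearby noun for a person. The participant is the natural antecedent. The person responsible for the leak is possible but less likely.

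**What the plan's sample size implies.** Section 1.5 says that the investigators "calculated a reasonable sample size using mean and standard deviation of the data", "assuming a mean difference of 5% type I error and 80% power". It prints neither the difference nor the standard deviation, so n=20 cannot be reproduced. For illustration I inverted it, assuming a two-sided 5% test of two means:

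- d = (1.960 + 0.842) × √(2/20) = 0.886 standard deviations. Putting d back gives 2 × (2.802/0.886)² = 20 per group.
- The margin over the calculated size is 25 − 20 = 5 per group, or 5/25 = 20%. Ordinary dropout comes out of the same margin.

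**Power after removals.** Power = Φ(d / √(1/n₁ + 1/n₂) − 1.960). The equivalent equal group size is 2n₁n₂/(n₁ + n₂).

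| Groups compared | Equivalent n per group | Power |
|---|---|---|
| 25 v 25 | 25.0 | 88% |
| 25 v 19 | 2×25×19/44 = 21.6 | 83% |
| 25 v 17 | 2×25×17/42 = 20.2 | 80% |
| 25 v 15 | 2×25×15/40 = 18.8 | 77% |
| 25 v 10 | 2×25×10/35 = 14.3 | 66% |
| 19 v 19 | 19.0 | 78% |
| 15 v 15 | 15.0 | 68% |

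The noncentral t, with d = 0.909, gives values within about one percentage point of these. A loss confined to one group must exceed 8 before the comparison falls below 80%: at 25 v 16 the equivalent size is 2×25×16/41 = 19.5. If both groups lose people equally, a sixth loss from each is enough.

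**How many could lose samples at one time.** Section 1.3 C sets participation at 12 weeks, and section 4.3 C expects 50 MS patients over one year. If accrual is even (an assumption), 25 × 12/52 = 5.8, so about 6 people per MS group are in follow-up at any moment. Of these, about 5.8 × 8/12 = 3.8 still owe both later samples and 5.8 × 4/12 = 1.9 owe only week 12. Bunched accrual would raise the number; 25 is the ceiling, reached only if a whole group is in follow-up together.

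**Limit of the arithmetic.** These figures describe a two-group comparison. The plan gives no basis for calculating power for the before-and-after comparison in section 1.3 D.

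**The case against.** The strongest reply is that this is one loosely worded sentence about an unlikely event, with no demonstrated effect on the planned analysis. Much of that stands.

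- A reader might infer that one lost device would delete a whole group. The documents do not support this. The text speaks of removal and does not mention erasing data. Section 6.2 does not say that files hold group lists or identifiers, and it specifies encryption and passwords. Anyone past week 12 has already given every scheduled sample.
- A reader might infer that 25 falling to 19 takes the study below the n=20 it calls sufficient. That figure is for each of two groups. With the other group intact, 25 v 19 is equivalent to 21.6 per group.
- A reader might infer that people taking HFS would lose safety contact, or that staff would be tempted not to report a leak. Both are conjecture. Section 6.3 C ties side-effect monitoring to people on HFS, and a person removed would presumably stop receiving it.
- A reader might infer that Group E would lose its source. Section 1.8 invites enrolled MS participants who relapse during or after the study; whether a removed person could still be invited is not stated.
- Consent pages are not in the public file and may describe notification after a breach.

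None of this rescues the clause. Consent wording on notification would not cancel a protocol rule that mandates removal. If *they* means whoever caused the leak, the section states no response for participants at all and still needs rewriting.

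**Conclusion.** The point holds as a defect in a stated rule. On its natural reading, section 6.3 H takes participants out of the study because the study failed to protect their information, without containing the leak and with no limit on numbers. The likely cost is modest: about 6 people per MS group in follow-up at one time under even accrual. That leaves power near 83% if one compared group is affected and 78% if both are, against 88% with full groups. Larger losses need bunched accrual and an event that exposes many records. These figures rest on a standardised difference of 0.886 inverted from n=20, a two-sided test and no other dropout. The case for change rests mainly on the rule serving no protective purpose and being cheap to replace.

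**What to change.** Delete the mandatory removal clause in section 6.3 H. State in its place that a suspected leak leads to:

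- suspension of the transfer route concerned;
- a report to the IRB and the institution's privacy office;
- notice to each affected participant, who then chooses whether to continue;
- retention of samples and data already collected, as agreed at consent.

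The adverse-reaction rule in the same section is a separate matter and is not touched by this change. The cost is one paragraph and a check that the consent wording agrees.
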